6.5 POOLING OF CENTERS

Endpoints will not be analysed by centre.

6.6 HANDLING OF MISSING DATA AND OUTLIERS

Based on the different reasons of patients' data missing for different endpoints, various methods will be used to assess the impact of missing data on the efficacy endpoints of this trial, depending upon the type of the endpoint (see [Table 6.3: 1](#)).

6.6.1 Definition of antidiabetic rescue therapy for censoring

For some of the imputation methods defined below, values after antidiabetic rescue medication will be set to missing. In this context, the following two situations are defined as use of antidiabetic rescue medication:

- Additional antidiabetic medication used for ≥ 7 consecutive days
- Change in dose of antidiabetic background medication for ≥ 7 consecutive days

This approach will be used when considering which data to exclude from the OC and LOCF analyses. For the definition of antidiabetic rescue therapy as a further endpoint, please refer to [Section 5.3.1](#).

For some other imputation methods, values after antidiabetic rescue and/or antihypertensive medication will be set to missing. For details on antihypertensive medication, refer to [Section 5.3.2](#).

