According to the drug assignment planned in this trial, 1/2 (50.0%) of patients participating in this trial may derive a direct benefit from being treated with an additional active compound and not a placebo. The patients will receive empagliflozin at doses which have demonstrated favorable HbA1c, glucose and BP changes multiple phase II and phase III studies [[c01678844](#)]. Patients in the placebo group (50.0%) have a higher probability of not getting an additional treatment benefit, i.e. no reduction in FPG or HbA1c values or no reduction in BP due to the absence of an additional treatment. However, the placebo arm is required for this study and is acceptable up to 31 weeks given that diet and exercise instructions are provided to the patients and they are monitored and if necessary rescued properly for significant hyperglycemia or high blood pressure. The patients enter the study in a stable condition with regard to glucose control for at least 12 weeks and BP control for at least 4 weeks before randomisation and appropriate criteria for rescue therapy ([Section 4.2.1](#)) or patient discontinuation ([Section 3.3.4](#)) will ensure an adequate treatment in case of any clinical concern.

Because of the mechanism of action of empagliflozin, the risk of hypoglycemic episodes is low. The incidence of hypoglycemia was slightly higher for empagliflozin treated patients compared with placebo in patients treated on backgrounds of sulfonylurea (SU) or insulin. However, the observed difference was not due severe hypoglycemia. Symptoms attributed to hypo- or hyperglycemia, as well as hypo- or hypertension will be closely monitored in the trial.

Special attention will be paid to monitor for diabetic ketoacidosis (DKA). A potential risk for DKA has been reported by the Food and Drug Administration (FDA) in patients treated with SGLT2 inhibitors, including empagliflozin. In a number of reported cases, the presentation of the condition was atypical with only moderately increased blood glucose values, below 14 mmol/L (250 mg/dl).

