In the case of hypoglycemia and/or hypotension that may put the patient at risk (e.g. repeated symptomatic hypoglycemia or severe hypoglycemia, repeated syncope), appropriate adjustment of oral antidiabetic and/or antihypertensive therapy such as a dose reduction / discontinuation of ongoing rescue medication or existing therapy should be initiated. Reduction or discontinuation of ongoing rescue medication should be considered before a reduction in the dose of existing therapy.

If, in the Investigator's clinical opinion, no further effect from the rescue medication is anticipated, and the patient's hyper- or hypoglycemia, and/or hyper- or hypotension cannot be controlled, the patient should discontinue the trial medication as specified in [Section 3.3.4](#).

Any rescue medication will be recorded in the source documents and on the appropriate pages of the eCRF.

Rescue medication will not be provided as part of the clinical trial supplies, unless required by local laws and regulations.

Any additional treatment that does not qualify as a rescue medication and is considered necessary for the patient's welfare may be given at the discretion of the Investigator. Exceptions to this are the restrictions described in Section 4.2.2.

There are no special emergency procedures to be followed.

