7.4 HANDLING OF MISSING DATA

Mixed Model Repeated Measures (MMRM) models and ANCOVA models including a LOCF imputation of missing data are used like discussed above in [Section 7.3.1](#) and [Section 7.3.2](#). The mixed effect model will handle missing data based on a likelihood method under the "missing at random assumption". Efficacy data will be censored at the date of first intake of antidiabetic rescue medication for all analyses, i.e., will be set to missing, if not explicitly stated otherwise.

Blood pressure data will additionally be censored from the day of change in antihypertensive therapy.

With respect to safety evaluations, it is not planned to impute missing values.

Further details will be provided in the TSAP.

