6.6.2.2 Observed cases (OC) analysis

For all efficacy endpoints, it is planned to analyse only the available data that were observed while patients were on-treatment, i.e., excluding the missing data. In other words, OC analysis will be performed and missing data in this analysis will not be replaced.

For all efficacy endpoints, this OC-technique will set all values measured after antidiabetic rescue medication to missing (antidiabetic rescue medication as defined in [Section 6.6.1](#)).

For BP endpoints, the OC-technique will be adapted to set values measured after antidiabetic rescue medication and/or a change in antihypertensive therapy to missing (see [Section 5.3.2](#) for the definition of a change in antihypertensive therapy). This technique will be called OC without values following a change in antihypertensive therapy (OC-H).

OC-H: For ABPM endpoints using data from two calendar days, no data will be excluded if the 24h collection starts before rescue medication or a change in antihypertensive therapy.

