6.6.2.7 Non-completers considered failure (NCF)

For binary endpoints, like a treat to target response of HbA_{1c} <7.0%, a conservative method to replace missing values is to consider them as "failures". Missing data due to early discontinuation will be replaced as "failure" (e.g. HbA_{1c} ≥ 7.0%) up to the planned final visit to be reached by all patients. Values obtained after antidiabetic rescue medication was started are also replaced as "failure".

For BP endpoints, values obtained after antidiabetic rescue medication and/or a change in antihypertensive therapy will be replaced as “failure”. This adaptation of the NCF technique will be called NCF without values following antidiabetic rescue medication and/or a change in antihypertensive therapy (NCF-H).

For binary endpoints that are derived from quantitative endpoints (e.g. HbA_{1c}), missing values within a course of measurements on-treatment will be replaced on the basis of the corresponding imputed value of the underlying quantitative endpoint (interpolation for HbA_{1c}).

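### SAP 6.6.1 sets no direction for background dose changes, so a reduction for hypoglycaemia lasting 7 days or more counts as rescue and, on the natural reading, as responder failure

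*SAP*

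**What the plan says.** SAP 6.6.1 treats two situations as use of antidiabetic rescue medication: "Additional antidiabetic medication used for ≥ 7 consecutive days" and "Change in dose of antidiabetic background medication for ≥ 7 consecutive days". The second limb has a duration threshold but no direction and no reason for the change. On scope, the section says: "This approach will be used when considering which data to exclude from the OC and LOCF analyses".

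The consequences differ by method. In OC (SAP 6.6.2.2, which cites 6.6.1), "this OC-technique will set all values measured after antidiabetic rescue medication to missing". LOCF (6.6.2.4) blanks the same values and then imputes them. NCF (6.6.2.7), used for binary efficacy endpoints, reads: "Values obtained after antidiabetic rescue medication was started are also replaced as" failure. NCF-H applies the same treatment to binary blood pressure endpoints.

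The protocol describes two different events. Section 4.2.1 allows antidiabetic rescue only for confirmed hyperglycaemia, by adjusting current therapy or adding a drug. For hypoglycaemia that may put the patient at risk, the same section calls for adjustment of therapy, "such as a dose reduction / discontinuation of ongoing rescue medication or existing therapy should be initiated". Protocol 7.4 says: "Efficacy data will be censored at the date of first intake of antidiabetic rescue medication for all analyses", unless explicitly stated otherwise, and leaves further detail to the SAP.

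**The concern.** A dose reduction for low glucose and a rescue for high glucose are opposite events, yet the dose-change limb of SAP 6.6.1 gives them one code. The situation is foreseeable. Sulfonylurea background is eligible (protocol 3.3.2), all patients are escalated at Week 4, and reductions of study drug are not permitted (protocol 4.1.4). Protocol 2.3 also reports: "The incidence of hypoglycemia was slightly higher for empagliflozin treated patients compared with placebo in patients treated on backgrounds of sulfonylurea (SU) or insulin".

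The clearest consequence is in the responder analyses. Scoring rescue as failure makes sense when rescue signals insufficient glucose lowering. A patient whose background drug was cut because glucose ran low, and who is still below 7.0%, has shown no such insufficiency, but the observed success would be replaced by a failure. If reductions are more frequent on empagliflozin, the responder comparison is pulled against that arm.

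**Working it through.** **Step 1: the texts side by side.**

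| Event | Protocol 4.2.1 | Protocol 7.4 | SAP 6.6.1 |
|---|---|---|---|
| Drug added, or background raised, for confirmed hyperglycaemia | Rescue | Censored | Rescue if 7 days or more |
| Background lowered for hypoglycaemia | Separate event, not rescue | Not named | Rescue if 7 days or more |

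The second row is the discrepancy. Reductions shorter than 7 consecutive days are not caught.

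**Step 2: does the definition reach NCF?** OC cites 6.6.1. NCF uses the term antidiabetic rescue medication without a citation, and 6.6.1 names only OC and LOCF. SAP 6.6.1 points to Section 5.3.1 for rescue as an endpoint, but that section is not in the public copy. With 6.6.1 the only visible definition, applying it to NCF is the natural reading, though not a certain one.

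**Step 3: size in the responder analysis.** The planned arm size is 77 (protocol 7.6). One true responder recoded as failure costs 1/77 = 0.013, or 1.3 points, if all 77 are in the denominator.

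The documents give no frequency of reductions. As an assumption, let a share r of the empagliflozin arm have a reduction of 7 days or more, and let 50% to 90% of those patients be true responders. Patients affected = 77 × r. Loss in responder rate = r × 50 to r × 90 points.

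| r (assumed) | Patients of 77 | Loss in responder rate (points) |
|---|---|---|
| 1% | 0.8 | 0.5 to 0.9 |
| 3% | 2.3 | 1.5 to 2.7 |
| 5% | 3.9 | 2.5 to 4.5 |
| 10% | 7.7 | 5.0 to 9.0 |

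**Step 4: precision of the primary analysis, for context.** Protocol 7.6 states power above 85% for a 0.6% HbA1c difference with SD 1.1%. With 64 per arm and two-sided 5%, the normal approximation gives Φ(0.6/1.1 × √(64/2) − 1.96) = Φ(1.13) = 87.0%, and the t-test gives 86.5%. The plan's figure is reproduced. Removing a share r of the empagliflozin arm only, for r of 1%, 3%, 5% and 10%, gives t-test power of 86.3%, 86.0%, 85.6% and 84.6%. This treats censored patients as contributing nothing. The MMRM still uses their earlier visits, so the true loss would be smaller.

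**The case against.** **Scope.** SAP 6.6.1 limits itself to OC and LOCF, and the unseen Section 5.3.1 may define rescue differently. This stands as an uncertainty. It means the scoring as failure cannot be reported as settled fact, but it is also a reason for the SAP to say which definition NCF uses.

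**Censoring any background change is legitimate.** Protocol 3.1 asks for unchanged antidiabetic dosage throughout. SAP violation D3.01 excludes any background dose change from the per-protocol set, in either direction. Protocol 7.4 censors blood pressure at any change in antihypertensive therapy, again without direction, and leaves detail to the SAP. Setting aside values after a background change is therefore a coherent strategy. This stands in full for OC and LOCF. It does not carry over to NCF, which replaces the observed value with the worst outcome.

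**A sensitivity analysis probably exists.** Table 6.3:1 lists OC-IR for the primary and key secondary endpoints. Its definition is not visible, but LOCF-IR is defined as including values after rescue, so OC-IR probably retains these observations. That helps the continuous endpoints. The table shows only NCF and NCF-H for the binary ones.

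**Small numbers and low stakes.** Protocol 2.3 calls the hypoglycaemia risk low and the sulfonylurea or insulin difference slight. Protocol 4.2.1 has ongoing rescue medication considered for reduction before existing therapy. No confirmatory endpoint is binary. All of this stands and limits the weight of the point.

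**Conclusion.** The definition is wider than the protocol's meaning of rescue, because it gives the dose-change limb no direction. On the natural reading of NCF, an observed HbA1c below 7.0% after a background reduction of 7 days or more becomes a failure, at 1.3 points of responder rate per patient in an arm of 77. How many patients this affects is unknown. The table in the working shows assumed rates only, and the conclusion depends on NCF taking its definition from 6.6.1.

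A reader might go further and infer that the primary MMRM is biased against empagliflozin. The documents do not support that. The censored values were measured on reduced background therapy, so keeping them may understate the drug effect and dropping them could favour the arm with more reductions. HbA1c values from before the reduction stay in the model. One could also calculate that deleting the best-responding 1% to 4% of the active arm shifts its mean HbA1c by 0.03% to 0.10%. That assumes the affected patients have the arm's lowest week-24 values after their background was cut, and nothing in the documents shows this. For OC and LOCF the point is one of definition and labelling only.

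**What to change.** For NCF and NCF-H, restrict the dose-change limb to an increase in background antidiabetic dose. Values observed after a reduction or stop would then be used as observed. State in SAP 6.6.2.7 which rescue definition applies.

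For OC and LOCF (and OC-H and LOCF-H), reconcile 6.6.1 with protocol 4.2.1 and 7.4 by stating whether reductions are censored. Either choice is acceptable. If they are censored, label them as a background change and not as rescue.

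The cost is a short SAP revision and one programming flag, settled before unblinding. The flag needs only the direction of change, which follows from the dose records; SAP 6.6.4 already handles partial dose-change dates. The reason for each change need not be captured. There is a small downside: HbA1c observed after a background reduction may slightly understate the drug effect. The change concerns analysis coding only and leaves patient management as it is.

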6.6.2 Imputation methods

6.6.2.1 Original result (OR) analysis

OR analysis implies the analysis of data exactly as observed. OR analysis will be performed on endpoints that are either not affected by antidiabetic rescue medication and/or change in antihypertensive therapy or if it is not meaningful to apply any imputation rule for replacing the missing values.

6.6.2.2 Observed cases (OC) analysis

For all efficacy endpoints, it is planned to analyse only the available data that were observed while patients were on-treatment, i.e., excluding the missing data. In other words, OC analysis will be performed and missing data in this analysis will not be replaced.

For all efficacy endpoints, this OC-technique will set all values measured after antidiabetic rescue medication to missing (antidiabetic rescue medication as defined in [Section 6.6.1](#)).

For BP endpoints, the OC-technique will be adapted to set values measured after antidiabetic rescue medication and/or a change in antihypertensive therapy to missing (see [Section 5.3.2](#) for the definition of a change in antihypertensive therapy). This technique will be called OC without values following a change in antihypertensive therapy (OC-H).

OC-H: For ABPM endpoints using data from two calendar days, no data will be excluded if the 24h collection starts before rescue medication or a change in antihypertensive therapy.

6.6.2.4 Last observation carried forward (LOCF)

An alternative method for quantitative endpoints is to replace missing values of a patient by her/his last observed measurement on-treatment.

The last observation on-treatment need not necessarily be a value selected as a visit value if multiple measurements were performed within a time window for a visit. In this case the last on-treatment value within the time window will be carried forward, while the visit value can be the value that was observed closest to the planned visit date or the first value observed in the time window (see [Table 6.7: 2](#) for further details).

Missing values within a course of measurements on-treatment will be interpolated based on the last observed value before the missing visit and the first observed value after the missing visit. This is independent from the selection of a value as the picked visit value to be used in the descriptive analysis by visit.

Let:

D_0 = date of a visit with a missing endpoint value;

D_1 = date of the next visit (with endpoint value non-missing) after the visit with missing endpoint;

D_{-1} = date of a previous visit (with endpoint value non-missing) before the visit with missing endpoint;

E_i = endpoint values for visits D_{-1} , D_0 , D_1 for $i = -1, 0$ and 1 .

Then the missing endpoint value can be interpolated as:

[figure not shown]
$$E_0 = E_{-1} + ((E_1 - E_{-1}) \times (D_0 - D_{-1}) / (D_1 - D_{-1})).$$

In general, the values measured after antidiabetic rescue medication was taken during the active treatment period by the patients will be set to missing; and these missing values will be imputed by LOCF technique.

For BP endpoints, the values measured after antidiabetic rescue medication and/or a change in antihypertensive therapy will be set to missing before being imputed by LOCF technique. This adaptation of the LOCF technique will be called LOCF without values following antidiabetic rescue medication and/or a change in antihypertensive therapy (LOCF-H).

Missing data will only be imputed up to the planned visit to be reached by all randomised patients (week 24).

LOCF-H: For ABPM endpoints using data from two calendar days, no data will be excluded if the 24h collection starts before rescue medication or a change in antihypertensive therapy.

6.6.2.7 Non-completers considered failure (NCF)

For binary endpoints, like a treat to target response of HbA_{1c} <7.0%, a conservative method to replace missing values is to consider them as "failures". Missing data due to early discontinuation will be replaced as "failure" (e.g. HbA_{1c} ≥ 7.0%) up to the planned final visit to be reached by all patients. Values obtained after antidiabetic rescue medication was started are also replaced as "failure".

For BP endpoints, values obtained after antidiabetic rescue medication and/or a change in antihypertensive therapy will be replaced as “failure”. This adaptation of the NCF technique will be called NCF without values following antidiabetic rescue medication and/or a change in antihypertensive therapy (NCF-H).

For binary endpoints that are derived from quantitative endpoints (e.g. HbA_{1c}), missing values within a course of measurements on-treatment will be replaced on the basis of the corresponding imputed value of the underlying quantitative endpoint (interpolation for HbA_{1c}).

6.6.3 Safety and other variables

Missing safety data will not be replaced.

An analysis of the changes from pre-treatment/baseline to the last available value under treatment and the minimum/maximum after pre-treatment/baseline will be determined for quantitative safety laboratory variables.

6.6.4 Missing dates and times

Missing or partial date information for AEs will be replaced according to general BI rules described in the BI guidance for handling of missing and incomplete AE dates (2).

If the date of first drug administration is missing but the patient was randomised, the date of the first drug administration will be set to the date of randomisation. If the date of first administration is partially missing with the month and year present, the day will be set to the date of randomisation if randomisation was in the same month. If randomisation was in the month prior to the first drug administration the missing day will be imputed as the first day of the month. A missing time of first drug administration will be imputed as 12:00 o'clock, missing administration times at on-treatment visits will be imputed by 12:00 o'clock.

As a general rule a missing drug stop date will be imputed according to the following principles:

- If an EoT visit or visit 7.2 is documented, it should be the date of the EoT visit.
- If the patient is lost to follow-up it should be the date of the last visit + the longest treatment duration based on drug supply + 1 day.
- If a patient died during the course of the trial and no additional information about drug stop date are available, the date of death will be used as drug stop date assuming that the patient took the medication until the day of death.

All other cases need to be assessed by the trial team on an individual basis, trying to use the points above as guidance.

If only the year of birth is known, the day and month of birth will be imputed as 01 January. For other incomplete date information always the midpoint of the possible interval will be used. If only the year is present the day and month will be imputed as 01 July, if year and month is present the day will be imputed as 15. If the year is missing, the date will be considered missing.

For partial start and stop dates (and dose change) for concomitant therapies (CT) and additional antidiabetic drugs the following derivations will be used to impute 'worst case' values:

- If the day of the end date is missing then the end date is set to last day of the month.
- If the day and month of the end date are missing then end date is set to 31 December of the year.

- If the day of the start date is missing the start date is set to first day of the month.
- If the day and month of the start date are missing then the start date is set to 01 January of the year.

All other cases need to be assessed by the trial team on an individual basis, using the above points as guidance.

6.7 BASELINE, TIME WINDOWS, AND CALCULATED VISITS

With regard to efficacy and safety endpoints, the term “baseline” refers to the last observed measurement prior to administration of any randomised study medication.

In general, the date and clock time of the first drug administration will be used to separate pre-treatment from on-treatment values; a notable exception to this rule is HbA_{1c} for which only the date will be used. Measurements taken after the first intake of randomised trial drug will be considered on-treatment values if they have been obtained up to end of the parameter specific follow-up period as defined in Table 6.7:1 below and will be assigned to the randomised trial drug for efficacy analyses and to the first trial drug taken for safety analyses.

Table 6.7: 1 Endpoint specific follow-up period for the assignment to active treatment

Endpoint	Last day of assignment to treatment phase (days after trial drug stop date)
Efficacy	
HbA _{1c}	7
FPG	1
Body weight	1
BP	1
HR	1
Waist circumference	7
Safety	
AEs	7
Safety laboratory measurements	3

Measurements taken after the end of the endpoint specific follow-up period and after the last intake of trial drug will be considered post-treatment values.

Table 6.7: 2 Time windows for on-treatment efficacy measurement scheduled for each on-treatment visit

Visit number	Visit label	Planned days	Time window (actual days on treatment)	
			Start	End ^A
3	Baseline	0	NA	1 ^B
4	Week 4	28	2	56
5	Week 12	84	57	105
6	Week 18	126	106	147
7	Week 24/EOT	168	148	Trial drug stop date + X days

^A In case of premature discontinuation of the trial drug a Visit 7.2 has to be performed. If such a Visit 7.2 falls into the time window of a previous visit, measurements will be assigned to this previous visit and the visit value will be determined as described below. In this case the time window for the visit that includes Visit 7.2 will end X days after the trial drug stop date, including Day X. The definition of X is endpoint specific, cf. [Table 6.7: 1](#). No time window for optional visit is planned.

^B Only values taken prior to the start of treatment with randomised trial drug will be considered baseline values. Time windows will be used for assignment of measurements to scheduled visits.

Reasons to base the time windows on the actual treatment start date rather than the randomisation date are:

- If first intake of trial drug shows a large delay by e.g. more than one week after the date of randomisation, a measurement taken four weeks after randomisation rather reflects the drug effect after three weeks than after four weeks and thus may underestimate the treatment effect at this visit.
- With large delays of the introduction of trial drug after the randomisation, the time window for the first on-treatment visit could include times the patient was not yet on trial drug.

The time window for the first visit after randomisation starts on the day after the first intake of trial drug. This maximises the number of measurements used in by visit analyses.

The midpoint between two on-treatment visits defines the end of a time window, with the midpoint being included in the time window of the preceding visit. The end of the time window of the last on-treatment visit (EoT) is endpoint dependent (see [Table 6.7: 1](#)).

For variables where only one on-treatment value is obtained at the EoT visit the time window for the EoT visit, and only one on-treatment measurement, will begin at the midpoint between first and last on-treatment visit (day 168). For patients with no on-treatment value on or after day 168 they will have no on-treatment measurement assigned in the OC approach. For the LOCF imputation, the last value on-treatment will be carried forward regardless of whether before day 168.

Repeated and unscheduled efficacy and safety measurements will be assigned to the nominal visits and listed in the subject data listing (SDL) according to the time windows described above. Only one observation per time window will be selected for analysis at an on-treatment visit - the value will be selected which is closest to the protocol planned visit day. If there are two observations which have the same difference in days to the planned day or if there are two observations on the same day, the first value will be used. If an observation is available on the last day of treatment, this observation will be preferably selected over any later observation that is still within the time window (not applicable for standard laboratory summaries). If there are multiple values within the time window of the last visit, including a value on the last day of drug intake, the value on the last day of drug intake is used as the value of the last visit.

For ABPM data only the first available successful ABPM reading at each of the ABPM time points (Visit 2.2, 5.1 and 7.1) will be used and not the closest to the protocol planned day. Data from a repeated second reading after a successful one at the same ABPM time point will be ignored for the analysis as no second reading should be conducted after one successful first attempt according to protocol and eCRF description.

Note: For LOCF imputation, the last observed on-treatment value will be carried forward within the applicable period, whether or not it was selected in the previous time window. For interpolation only selected values are to be used. For more details on LOCF refer to [Section 6.6](#).

